5. INVESTIGATIONAL PLAN

5.1. Overall Design and Plan of Trial

This is a phase I study that will evaluate imaging characteristics of ¹⁸F-AV-1451 in subjects with Frontotemporal Dementia (FTD).

Subjects followed in a referral center research cohort for FTD will be contacted to participate and must provide informed consent before starting any ¹⁸F-AV-1451-A19 study procedures. Diagnosis will be determined by companion study with detailed characterization provided by enrolling physician. Screening assessments may take place over several days and will include demographic information, a medical assessment for eligibility, ECG a brief cognitive assessment (e.g. MMSE), and florbetapir F 18 Positron Emission Tomography (PET) imaging. The screening florbetapir F 18 PET scan is to be performed to assess for evidence of amyloid pathology and should be interpreted by the local reader prior to enrollment.

Subjects who qualify for the study will come to the imaging center at a later date and will have a catheter(s) placed for IV administration of ¹⁸F-AV-1451. Vital signs will be taken in a supine position immediately prior to administration of ¹⁸F-AV-1451 (within 30 minutes prior to injection) and at the completion of imaging prior to subject discharge. Subjects will receive up to a target dose of 370 mBq as a single IV bolus of ¹⁸F-AV-1451. A 30 minute dynamic image starting approximately 75 minutes post injection will be obtained.

Adverse events will be continuously monitored during the imaging sessions. Subjects who experience any adverse event will not be discharged until the event has resolved or stabilized.

A follow-up phone call to the subject, or designated decision maker, will be conducted between 2 or 3 business days, but not less than 48 hours, after each imaging visit, to confirm subject well-being and to collect information about any new adverse events.

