- Death;
- Initial or prolonged inpatient hospitalization (other than that required by protocol; “social hospitalization” or any hospitalization for non-medical reasons does not constitute a SAE);
- A life-threatening experience (that is, immediate risk of dying);
- Persistent or significant disability/incapacity;
- Congenital anomaly/birth defect;
- Considered significant by the investigator for any other reason.

Important medical events that may not result in death, be life-threatening, or require hospitalization may be considered serious adverse drug events when, based upon appropriate medical judgment, they may jeopardize the patient and may require medical or surgical intervention to prevent one of the outcomes listed in this definition.

Unexpected Adverse Event

An unexpected adverse event is an adverse event not previously reported or an adverse event that occurs with specificity, severity or frequency that is not consistent with the current IB.

Relationship to Study Drug

Investigators will be instructed to report their assessment of the potential relatedness of each adverse event to protocol procedure or study drug. The assessment of the relationship of an adverse event to the administration of the study drug is a clinical decision based on all available information at the time of the completion of the eCRF.

Intensity/Severity of an Adverse Event

Protocol ¹⁸F-AV-1451-A19: “¹⁸F-AV-1451 PET Imaging in Subjects with Frontotemporal Dementia”

In addition to assessing the relationship of the administration of the study drug to adverse events, an assessment is required, in order to determine the intensity (severity) of the event.

The following classifications should be used:

Mild:

A mild adverse event is an adverse event, usually transient in nature and generally not interfering with normal activities.

Moderate:

A moderate adverse event is an adverse event that is sufficiently discomforting to interfere with normal activities.

Severe:

A severe adverse event is an adverse event that incapacitates the subject and prevents normal activities. Note that a severe event is not necessarily a serious event; nor must a serious event necessarily be severe.

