8.2.2. Safety Analyses

Adverse events including injection site reactions will be summarized in terms of number and percentage of patients experiencing an AE. The AEs will be summarized by system organ class (SOC) and preferred term using Medical Dictionary for Regulatory Activities (MedDRA) terms. Adverse events will also be presented by severity, relationship to treatment, and seriousness. All patients who experience SAEs, or who discontinue due to AEs, will be summarized.

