6.6.2 Adverse Events

All adverse events (AEs) occurring after signing the informed consent are to be recorded on the AE pages of the case report form (CRF). Any pre-existing conditions (i.e., undesirable experiences, signs or symptoms that begin prior to the Screening Visit) will be recorded on the medical history eCRF pages. The investigator's verbatim term of AEs will be mapped to SOC and PT using the MedDRA v 21.1 or higher.

Adverse Events:

An AE is any undesirable experience occurring to a subject during a clinical trial, whether or not considered related to the study drug. In this study clinically relevant abnormal finding, as well as worsening of any pre-existing condition shall be recorded as an AE. AEs that occur after administration of either drug but outside 48 hour reporting window will not be reported unless those are attributed to the study drug.

Unexpected Adverse Events:

An unexpected adverse event is an adverse event not previously reported or an adverse event that occurs with specificity, severity or frequency that is not consistent with the current Investigator's Brochure (IB).

Serious Adverse Events (SAEs):

Serious AEs (SAEs) are events that result in one of the following outcomes or constitute one of the following events:

- Death
- Initial or prolonged hospitalization
- A life-threatening experience (that is, immediate risk of dying)
- Persistent or significant disability/incapacity
- Congenital anomaly/birth defect
- Considered significant by the investigator for any other reason

Important medical events that may not result in death, be life-threatening, or require hospitalization may be considered serious adverse drug events when, based upon appropriate medical judgment, they may jeopardize the patient and may require medical or surgical intervention to prevent one of the outcomes listed in this definition.

For the summarization of AEs by seriousness, events recorded with missing seriousness will be summarized as serious, following worst case principle.

Trial Emergent Adverse Events:

Trial Emergent AEs are defined as any AEs that occur or worsen (increase in intensity and/or frequency) after the informed consent, and prior to administration of Florbetapir F 18, or between the Florbetapir F 18 injection session and Flortaucipir F 18 injection session but outside the 48 hours window following administration of Florbetapir F 18 or Flortaucipir F 18.

Treatment Emergent Adverse Events (TEAEs):

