TEAEs are defined as any AEs that occur or worsen (increase in intensity and/or frequency) after administration of Flortaucipir F 18 or Florbetapir F 18 and until 48 hours post administration.

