8.10.2 Adverse Events

All AE summary tables will include only TEAEs, unless otherwise specified.

Adverse events will be summarized by SOC and PT. A subject will only be counted once per SOC and PT.

For AEs by severity grade (mild, moderate, severe), if a subject has multiple events occurring in the same SOC or same PT, then the event with the maximum intensity (i.e. severe) will be counted.

For AEs by relationship to study drug and protocol procedure will be summarized as Related vs. Not Related. If a subject has multiple events occurring in the same SOC or same PT, the event associated with the study drug will be summarized.

AEs will be summarized by descending frequency, then alphabetically by SOC and preferred term.

An overall summary of AEs will be presented and will include:

- Subjects with any Trial Emergent AEs
- Subjects with at least one TEAE
- Subjects with any severe or moderate TEAE
- Subjects with any TEAE related to Florbetapir F 18
- Subjects with any TEAE related to Flortaucipir F 18
- Subjects with any TEAE related to protocol procedure
- Subjects with any serious TEAE
- Subjects with any TEAE resulting in death
- Subjects with any TEAE leading to study discontinuation

The following summary tables will be presented by SOC and PT:

- Trial Emergent AEs
- All TEAEs
- TEAEs by PT
- TEAEs by severity
- TEAEs by relationship to Florbetapir F 18
- TEAEs by relationship to ¹⁸F-AV-1451
- TEAEs by relationship to protocol procedure
- Serious TEAEs
- TEAEs resulting in death
- TEAEs leading to study discontinuation

The following listings will be presented by subject:

- All AEs
- Serious TEAEs
- TEAEs leading to study discontinuation
- TEAEs resulting in deaths

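### The procedure-relatedness summaries take only events after injection, so procedure-related AEs can be under-counted; the repeat-event rule leaves the procedure table undefined

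*SAP*

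**What the plan says.** SAP 8.10.2 sets a default: "All AE summary tables will include only TEAEs, unless otherwise specified". Its SOC/PT tables include "TEAEs by relationship to protocol procedure", and its overview has a row for subjects with at least one such TEAE. Trial-emergent AEs get one overview row and one SOC/PT table, neither split by relatedness.

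SAP 6.6.2 defines a TEAE as an event that starts or worsens "after administration of Flortaucipir F 18 or Florbetapir F 18 and until 48 hours post administration". A trial-emergent AE starts or worsens "after the informed consent, and prior to administration of Florbetapir F 18", or between the two imaging sessions but outside the 48 h windows.

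For repeat events in the same SOC or PT, one sentence in SAP 8.10.2 covers the drug and the procedure tables alike: "the event associated with the study drug will be summarized". SAP 6.6.2.1 defines drug relatedness by timing (any AE in the 48 h following a tracer) and leaves procedure relatedness to the investigator.

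On the protocol side, subjects "will have a catheter(s) placed for IV administration of" flortaucipir (Protocol 5.1), and an MRI may be done at screening (Protocol 7.1.1). Investigators are to "report their assessment of the potential relatedness of each adverse event to protocol procedure or study drug" (Protocol 7.7.2). Protocol 7.7.2 collects trial-emergent AEs in order to pick up harm from taking part. Protocol 7.7.4 has an SAE between consent and first dose reported only if a study procedure may have caused it.

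**The concern.** Some study procedures come before the injection that opens the TEAE window. An event from one of them is recorded with an investigator's judgement on procedure relatedness, but no summary uses that judgement. The sharpest case is the pre-dose SAE: under Protocol 7.7.4 it is reported only because a procedure may be the cause, and it then misses both the procedure table and the serious-TEAE table.

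The repeat-event rule is a second, separate gap. The severity rule in the same section selects on the factor being tabulated (maximum intensity). The relationship rule selects on drug association even when the table is about procedures.

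At stake is a safety summary in a small descriptive study whose secondary objective is safety. A low count in the procedure row could be read as meaning that procedures caused little harm, when the row excludes events that procedures before injection may cause.

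**Working it through.** The plan states no figure on this point, so there is nothing to reproduce. The check sets the definitions side by side and then enumerates the counting rule.

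**Step 1. Where a procedure-related event lands**

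| Start of event | Class under SAP 6.6.2 | In procedure row and table? |
|---|---|---|
| After consent, before florbetapir (e.g. on-study MRI) | Trial-emergent | No |
| Up to 48 h after florbetapir | TEAE | Yes |
| Between sessions, more than 48 h after florbetapir | Trial-emergent, if recorded as an AE | No |
| Flortaucipir session before injection (e.g. catheter placement), more than 48 h after florbetapir | Not clearly covered: the SAP window lies between the sessions | No |
| As above, but within 48 h of florbetapir | TEAE | Yes |
| Up to 48 h after flortaucipir | TEAE | Yes |

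Two details bear on the table. Subjects with a usable earlier amyloid scan get no study florbetapir (Protocol 7.1.1.1), so the florbetapir limits of the SAP's trial-emergent window have no date for them. Both documents also restrict reporting after a tracer but outside its 48 h window to events attributed to the drug, so the between-session group may be small. That restriction does not touch events before the first injection.

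**Step 2. The repeat-event rule**

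Take one subject with two post-injection events in one PT, order counted. Code each event as drug-related yes/no and procedure-related yes/no. The correct entry is Related if either event is procedure-related.

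*SAP 6.6.2.1 timing rule (both events drug-related).* There are 2 × 2 = 4 patterns, of which 4 − 1 = 3 contain a procedure-related event.
- Forced to Not Related: 0.
- Undetermined (one event procedure-related, the other not, and both qualify for selection): 2.
- Correctly Related: 3 − 2 = 1.

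*Investigator-judged drug relatedness (hypothetical).* There are 4 × 4 = 16 patterns, of which 16 − 4 = 12 contain a procedure-related event.
- Forced to Not Related (one event drug-related only, the other procedure-related only): 2.
- Undetermined (same drug status in both, exactly one procedure-related): 2 × 2 = 4.
- Correctly Related: 12 − 2 − 4 = 6.

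**Step 3. Both gaps together, timing rule**

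Let each of the two events also fall inside or outside the TEAE window. There are 4 × 4 = 16 patterns, and 16 − 4 = 12 contain a procedure-related event.
- Missed: 3 with both events outside the window, plus 2 with the only procedure-related event outside it, giving 5.
- Undetermined: 2.
- Correct: 12 − 5 − 2 = 5.

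No pattern gives an over-count. Missing relationships, which SAP 6.6.2.1 sets to related, were left out; they push the count up. These are counts of logical patterns, not probabilities.

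**Step 4. Size**

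If *k* subjects are affected among *N*, the row is low by 100 × *k*/*N* percentage points. With *N* = 25, *k* = 1 gives 1/25 = 4 points and *k* = 2 gives 2/25 = 8 points. Both values of *k* are assumptions. *N* is also uncertain, because the Safety Population includes anyone given florbetapir, and some of those may then be excluded as amyloid-positive. A larger *N* makes each subject count for less.

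**Step 5. After the change**

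With both AE classes in the table and an any-event rule, the entry is correct in every pattern (0 missed, 0 undetermined), provided that each event falls in one of the two classes.

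**The case against.** The strongest reply is that nothing is lost. Trial-emergent AEs have their own SOC/PT table and overview row, and every AE is listed. Limiting relationship tables to TEAEs is a stated and coherent choice. Protocol 8.2.2 promises AEs by relationship to treatment, not to procedure, and the secondary objective concerns the flortaucipir safety database. The protocol's specific commitment, "Adverse events including injection site reactions will be summarized", is met, because such reactions follow injection and are TEAEs. In a study of about 25 subjects a reader can go to the listing. This stands as a limit on importance: what is missing is the procedure attribution in the summaries, not the events.

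Three stronger readings are tempting, and the documents do not support them.

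- A reader might infer that procedure-related events will certainly be under-counted. The documents give no AE rates. Some events before the flortaucipir injection are TEAEs anyway: the scans need be only 16 h apart (Protocol 7.1.2), so catheter placement can fall within 48 h of florbetapir, and an event that worsens after injection also qualifies.
- A reader might infer that the repeat-event rule discards procedure-related events in favour of drug-related ones. Under SAP 6.6.2.1 every TEAE is drug-related, so the rule cannot prefer one over the other. A forced Not Related needs investigator-judged drug relatedness, which the SAP does not use. The overview row counts any event and does not need the rule.
- A reader might infer that the rule's singular reference to the drug leaves the two tracers confused. Separate tables and rows for each tracer largely settle which drug is meant.

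**Conclusion.** The point holds in two limited parts.

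1. On the text, procedure-related AEs that start before injection or outside the 48 h windows cannot enter either procedure-relatedness summary and can be under-counted there. This includes the pre-dose SAEs that Protocol 7.7.4 singles out as possibly caused by a procedure. They remain in the all-AE listing and, where SAP 6.6.2 covers them, in the trial-emergent table.
2. The repeat-event rule leaves the procedure table's SOC/PT entry undefined when one event is procedure-related and another is not. It does not affect the overview row.

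Apart from missing relationships set to related, any error is downward. Its size cannot be computed; 4 percentage points per affected subject assumes a denominator of 25. This is a cheap improvement to a descriptive safety summary and does not threaten the study's conclusions.

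**What to change.** Make two changes to SAP 8.10.2.

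1. State that the procedure-relatedness overview row and table include trial-emergent and treatment-emergent AEs in the Safety Population. Alternatively, keep the TEAE versions and add a table of trial-emergent AEs by procedure relatedness.
2. Replace the repeat-event sentence with: *In each relationship table, a subject is counted as Related within a SOC or PT if any of the subject's events there is related to the factor of that table (florbetapir, flortaucipir or protocol procedure).*

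For the first change to work fully, SAP 6.6.2 should say how it classes events in the flortaucipir session before injection, and events in subjects who get no study florbetapir. The trial-emergent definition in Protocol 7.7.2 already reaches up to dosing at the imaging visit.

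The cost is two sentences and at most one small extra table, on data already collected. The procedure-related count may rise slightly. Subjects who consent but are never dosed stay outside the Safety Population, so their events would still appear only in listings.

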8.10.3 Serum and Urine Pregnancy Test

Serum and urine pregnancy data will be presented in a listing for subjects in Safety Population.

8.10.4 Vital Signs

Vital signs (pulse, respiratory rate and supine blood pressure) including body weight will be summarized using descriptive statistics for observed and change from baseline values.

All vital signs data will be presented in the listing.

8.10.5 Electrocardiogram (ECG)

The ECG data collected at screening will be presented in the listing.

8.10.6 Follow-up Telephone Contact

A listing will be provided for information based on Follow-up Telephone Contact.

8.11 Pharmacodynamics

No pharmacodynamics analysis is planned for this study.

9 COMPUTER SOFTWARE

All analyses will be performed by Chiltern using SAS® Version 9.3 or later. All summary tables and data listings will be prepared utilizing SAS® software.

The standard operating procedures (SOPs) of Chiltern will be followed in the creation and quality control of all data displays and analyses.

